6 TREATMENTS

6.1 Investigational Product(s)

6.1.1 *Description of Investigational Product(s)*

Test Product

Substance: ATI-450

Strength: 50 mg

Mode of administration: Oral tablets

Placebo

Substance: Placebo

Strength: Not applicable

Mode of administration: Matching oral tablets

6.1.2 *Preparation, Handling, and Storage*

The investigator (or designee) is responsible for the safe and proper storage of study medication at the site. ATI-450 and placebo will be stored under controlled conditions according to the storage requirements described on the label(s).

6.1.3 *Packaging, Labeling, and Shipment*

ATI-450 and matching placebo will be packaged and labeled in accordance with all applicable regulatory requirements and Good Manufacturing Practice guidelines.

ATI-450 and matching placebo will be supplied in high-density polyethylene bottles.

Study medications will be shipped and stored under controlled conditions according to the storage requirements.

Refer to the pharmacy manual for full details for packaging, labeling, and shipment of the study medication.

The sponsor or designee will supply the study medications. MTX and folic/folinic acid will be obtained locally by the site.

6.2 Blinding

The investigators, study personnel, and the study patients will remain blinded to treatment allocation as will sponsor personnel responsible for monitoring the clinical data. The Aclaris statistician, medical and safety monitor will be unblinded to each patient's treatment allocation.

6.4 Dose and Administration

ATI-450 will be administered as oral tablets for a total of 100 mg daily. Doses will be administered BID (50 mg \times 2). Matching placebo tablets will be administered in the same manner.

6.5 Precautions and/or Lifestyle Considerations

There are no lifestyle considerations (such as dietary or physical activity restrictions) for this study.

6.7 Concomitant Medication

See [Section 4](#) for details of medication that is permitted or prohibited according to the inclusion and exclusion criteria.

A large black rectangular redaction box covers the majority of the page content, from approximately y=111 to y=250. The box is positioned below a thin black horizontal line at y=111 and above a thin black horizontal line at y=250. There are small black rectangular artifacts on the left and right edges of the redaction box, likely from the scanning process.

Category	Approximate Sample Count
1	1000
2	950
3	100
4	900
5	400
6	200
7	400
8	200
9	400
10	1000

6.8 Vaccine Guidelines

Vaccination with live or attenuated components is prohibited during the study and for 6 weeks after the last dose of study medication. Similarly, current routine household contact with children and others vaccinated with live or attenuated vaccine components should be avoided during treatment and for 6 weeks following completion of the study.

Some of these vaccines include varicella (“chickenpox”) vaccine, oral polio vaccine, and the inhaled flu vaccine.

Following vaccination with live or attenuated component vaccines, the virus may be shed in bodily fluids, including stool, and there is a potential risk that the virus may be transmitted. General guidelines suggest that exposure should be avoided following vaccination with these vaccines for the stated time period:

- Varicella or attenuated typhoid fever vaccination for 4 weeks following vaccination;
- Oral polio vaccination for 6 weeks following vaccination;
- Attenuated rotavirus vaccine for 10 days following vaccination;
- Inhaled flu vaccine for 1 week following vaccination.

6.9 Overdose

There is limited clinical experience with ATI-450. In the event of an overdose, patients should receive appropriate supportive medical care and be followed until resolution/stabilization of any clinical issues.

Any instance of overdose (suspected or confirmed and irrespective of whether or not it involved ATI-450) must be communicated to the sponsor (or a specified designee) within 24 hours of its occurrence.

Any overdose associated with clinical symptoms will be recorded as an AE or SAE, as appropriate. Details of any signs or symptoms and their management should be recorded, including details of any treatments administered for the overdose. All overdoses with clinical symptoms meeting the SAE criteria must be reported as described in [Section 7.4](#).

6.10 Compliance

The investigator (or designee) will explain the correct use of the study medication to each patient and will check that each patient is following the instructions properly.

Compliance will be assessed at each visit by counting returned tablets and will be documented in the source documents and eCRF. Any deviation from the correct use of the study medications will be recorded in the eCRF.

A record of the number of tablets (ATI-450 or placebo) dispensed to and taken by each patient will be maintained and reconciled with study medication and compliance records. The study medication start and stop dates, including dates for study medication delays and/or dose reductions, will also be recorded in the eCRF.

Weekly dose of MTX and folic/folinic acid will be recorded at the clinic visits in the eCRF.

6.11 Accountability

The study medication must not be used for any purpose other than that defined in this protocol. All supplies of study drug will be accounted for in accordance with Good Clinical Practice (GCP).

The pharmacist or (designee) should maintain accurate records of all study medication supplies received during the study. These records should include the dates and amounts of study medication that were received at the site, dispensed, and destroyed or returned to the sponsor (or designee). The records should include dates, quantities, batch/serial numbers, expiration dates (if applicable), and the unique code numbers assigned to the study medication and study patients. If errors or damage in the study medication shipments occur, the investigator should contact the sponsor (or its designee) immediately. Copies of the study medication accountability records will be provided by each investigator for inclusion in the trial master file (TMF). The study monitor will periodically check the supplies of study medication held by the investigator or pharmacist to verify accountability of the study medication used.

The investigator (or designee) will administer the study medication only to the identified patients in this study, according to the procedures described in this study protocol.

After the end of the study, all unused study medication and all medication containers should be destroyed at the study center or returned to the sponsor (or designee) for destruction. In either instance, complete documentation will be returned to the sponsor.

7 ADVERSE EVENTS

7.1 Definitions

7.1.1 *Adverse Events*

An AE is any untoward medical occurrence in a patient or clinical study patient administered a pharmaceutical product and which does not necessarily have a causal relationship with this treatment. An AE can therefore be any unfavorable and unintended sign (including an abnormal laboratory finding), symptom, or disease temporally associated with the use of a medicinal (investigational) product, whether or not related to the medicinal (investigational) product.

7.1.2 *Serious Adverse Events*

An SAE is any untoward medical occurrence that meets any of the following criteria:

- Results in death.
- Is life-threatening.
- Requires inpatient hospitalization or prolongation of existing hospitalization.
- Results in persistent or significant disability/incapacity.
- Is a congenital anomaly/birth defect.
- Is an important medical event that may not result in death, be life-threatening, or require hospitalization. The event will be considered an SAE when, based upon appropriate medical and scientific judgment, the event may jeopardize the patient and may require medical or surgical intervention to prevent one of the outcomes listed above. Examples of such events include: intensive treatment in an emergency room or at home for allergic bronchospasm, blood dyscrasias or convulsions that do not result in inpatient hospitalization, or the development of drug dependency or drug abuse.

Definition of Terms

Life-threatening: an AE is life-threatening if the patient was at immediate risk of death from the event as it occurred; i.e., it does not include a reaction that, if it had occurred in a more severe form, might have caused death. For example, drug-induced hepatitis that resolved without evidence of hepatic failure would not be considered life-threatening even though drug-induced hepatitis can be fatal. It does not include an AE or suspected adverse reaction that, had it occurred in a more severe form, might have caused death.

Hospitalization: AEs requiring hospitalization or prolongation of hospitalization should be considered SAEs. Hospitalization for elective surgery, or for procedures planned prior

to the patient providing informed consent, or routine clinical procedures that are not the result of an AE (e.g., elective surgery for a pre-existing condition that has not worsened) need not be considered AEs or SAEs. If anything untoward is reported during the procedure, that occurrence must be reported as an AE or SAE as per the definitions.

In general, hospitalization signifies that the patient has been detained (usually involving at least an overnight stay) at the hospital or emergency ward for observation and/or treatment that would not have been appropriate in the physician's office or outpatient setting. When in doubt as to whether hospitalization occurred or was necessary, the AE should be considered serious.

Disability/incapacity: an AE is incapacitating or disabling if the experience results in a substantial and/or permanent disruption of the patient's ability to carry out normal life functions.

7.1.3 *Clinical Laboratory Abnormalities and Other Abnormal Assessments*

Laboratory abnormalities without clinical significance should not be recorded as AEs or SAEs. However, laboratory abnormalities (e.g., clinical chemistry, hematology, coagulation, lipids, and urinalysis abnormalities) that require medical or surgical intervention or lead to study medication interruption, modification, or discontinuation must be recorded as an AE or SAE, as applicable. In addition, laboratory or other abnormal assessments (e.g., in ECGs, X-rays, or vital signs) that are associated with signs and/or symptoms must be recorded as an AE or SAE if they meet the definition of an AE or SAE as described in [Sections 7.1.1](#) and [7.1.2](#). If the underlying cause for the laboratory abnormality is known, record the etiology or diagnosis (e.g., anemia), rather than the laboratory result (i.e., decreased hemoglobin).

For specific information on handling of clinical laboratory abnormalities, see [Section 5.3.2](#).

7.2 *Assessment of Adverse Events*

7.2.1 *Severity*

The investigator will determine the intensity of the AE according to the definitions below:

- **Mild:** An event that is easily tolerated by the participant, causing minimal discomfort and not interfering with everyday activities
- **Moderate:** An event that causes sufficient discomfort and interferes with normal everyday activities
- **Severe:** An event that prevents normal everyday activities. An AE that is assessed as severe should not be confused with a SAE. Severe is a category utilized for

rating the intensity of the event; both AEs and SAEs can be assessed as severe. An event is defined as “serious” when it meets at least 1 of the pre-defined outcomes as described in the definition of an SAE, not when it is rated as severe.

7.2.2 *Causality*

The investigator is obligated to assess the relationship between study medication and each occurrence of an AE/SAE. The investigator will use her/his best clinical judgment to determine the relationship. Alternative causes, such as underlying disease(s), concomitant therapy, and other risk factors, as well as the temporal relationship of the event to study intervention administration will be considered and investigated. The investigator will also consult the IB in his/her assessment. The investigator will define the relationship of an AE to the study medication by selecting one of the following categories:

Related:

- There is a reasonable possibility that there is a causal relationship between the study medication and the AE

Not Related:

- There is no reasonable possibility that there is a causal relationship between the study medication and the AE

A “reasonable possibility” of a relationship conveys that there are facts, evidence, and/or arguments to suggest a causal relationship, rather than a relationship cannot be ruled out.

7.3 Documenting and Reporting Adverse Events

Reporting of SAEs will begin when the patient has provided informed consent and will continue up to the end of study visit or 30 days after the last study drug administration whichever is later. Reporting of AEs will begin when the patient receives the first dose of study medication and will continue up to the end of study visit or 30 days after the last study drug administration, whichever is later. Any clinical AE that occurs between the time of consent and dosing Day 1 will be recorded as medical history.

Occurrence of AEs may be volunteered spontaneously by the patient; discovered as a result of general, nonleading verbal questioning by the study staff; or determined by physical examination or other safety assessments. All AEs will be monitored and recorded in the CRF throughout the entire study.

For all AEs, the investigator must pursue and obtain adequate information (a description of the event, severity, time of occurrence [including whether the AE onset was before, during, or after the study medication administration if the AE started on a dosing day], duration, and any action, e.g., treatment/follow-up tests). The outcome of the event should be provided along with the investigator’s assessment of the relationship to the

study medication. The investigator must also assess whether the event meets the criteria for classification as an SAE.

It is the investigator's responsibility to review all documentation (e.g., hospital notes, laboratory reports, and diagnostic reports) related to an AE. Wherever possible, the investigator's diagnosis, not the individual signs and symptoms, will be documented as the AE.

Investigators are not obligated to actively seek AEs or SAEs after the patient's conclusion of study participation. However, if the investigator learns of any SAE, including death, at any time after a patient has been discharged from the study, and he/she considers the event to be reasonably related to the study medication or study participation, the investigator must promptly notify the sponsor.

7.4 Reporting of Serious Adverse Events

Upon becoming aware of a SAE whether or not related to the study medications, the investigator must:

1. Take the appropriate medical action to ensure the patient's safety.
2. Immediately, and no longer than within 24-hours, report the SAE to the safety monitor, ensuring that the patient information is de-identified to:
[REDACTED]
[REDACTED]
3. Print a copy of the email confirmation from [REDACTED] and place in the study file.
4. Within 24-hours complete, as fully as possible an SAE form; email the forms and any other relevant information (e.g., concomitant medication eCRF, medical history eCRF, laboratory test results) to [REDACTED] (Aclaris Therapeutics, Inc. safety monitor).
5. Monitor and document the progress of the SAE until it resolves or, if not resolved after the patient's last study visit, until in the opinion of the investigator the AE reaches a clinically stable outcome with or without sequelae AND the investigator and Aclaris Therapeutics, Inc. safety and medical monitor agree that the SAE is satisfactorily resolved.
6. Report any SAE updates within 24-hours of knowledge to the safety monitor via email (or fax) and update the SAE form.
7. Comply with the appropriate regulatory requirements and Aclaris Therapeutics, Inc. instructions regarding reporting of the SAE to the responsible IRB.

The investigator is obliged to respond to any request for follow-up information (e.g., additional information, event outcome, final evaluation, or other records where needed) or to any question the sponsor (or designee) may have concerning the SAE within the same timelines as those noted above for initial reports. This is necessary to ensure prompt assessment of the event by the sponsor (or designee) and, as applicable, to allow the sponsor to meet strict regulatory timelines associated with expedited reporting obligations for events of this nature.

7.5 Adverse Event and Serious Adverse Event Follow-up

During the study (and after the end of study visit), all AEs and SAEs should be followed proactively by the investigator until the event resolves or the condition stabilizes to a level acceptable to the investigator, until the event is otherwise explained, or until the patient is lost to follow-up. At the time the patient's study participation ends, all ongoing AEs and SAEs should be evaluated for resolution. New or updated information will be recorded in the originally completed eCRF and the investigator will submit any updated SAE information to the sponsor within 24 hours of receipt of the information.

7.6 Safety Reporting Oversight

In accordance with ICH GCP, the sponsor (or designee) will inform investigators of "findings that could affect adversely the safety of patients, impact the conduct of the trial, or alter the IRB/Independent Ethics Committee (IEC) approval/favorable opinion to continue the trial."

The sponsor has a legal responsibility to notify both the local regulatory authority and other regulatory agencies about the safety of a study medication under clinical investigation. The sponsor will comply with country-specific regulatory requirements relating to safety reporting to the regulatory authority, IRB/IEC, and investigators. To support compliance with these requirements, the investigator must provide requested information in a timely manner.

An investigator who receives an investigator safety report describing SAEs or other specific safety information (e.g., summary or listing of SAEs) from the sponsor will file it along with the IB and will notify the IRB/IEC, if appropriate, according to local requirements.

8 STATISTICS

8.1 General Procedures

Analyses will be performed using SAS® (SAS Institute, Cary, NC, US) by the sponsor or its representatives.

The statistical analysis plan (SAP) will be approved prior to any lock of the study database and unblinding of the study data. The SAP will provide a detailed description of the statistical methods and expand on the details provided in the protocol.

All data will be presented by treatment group. Descriptive statistics (number of observations, mean, standard deviation, median, minimum, and maximum) will be provided for continuous variables, and counts and percentages will be presented for categorical variables.

Baseline is defined as the last non-missing measurement before or on the date of first administration of study medication.

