During the screening period, each patient will be required to have all assessments performed as outlined in the Schedule of Assessments. The MRI is not to be performed until the site obtains the results of the patient's hsCRP level to ensure that this assessment meets the entry criteria prior to performing the MRI. The patient will have the RAMRIS Hand-Wrist MRI assessment performed at their local institution and evaluated by a central radiology review team to determine if they meet the radiological inclusion criteria. Results for all of the screening assessments must be available at the time patient eligibility is reconfirmed prior to randomization and dosing.

Patients whose eligibility is confirmed at baseline will be randomized in a 3:1 ratio to receive either ATI-450 tablets (50 mg twice daily [BID]) plus MTX, or matching placebo tablets plus MTX. Study medications will be administered orally for 12 weeks. Patients will be required to remain on a stable dose of MTX (7.5 mg to 25 mg/week) for the duration of the study.

Patients will attend clinic visits on Days 7, 14, 28, 42, 56, and 84 (± 1 day) for safety, efficacy, PK, and PD assessments. The morning dose of study medication will be administered in the clinic on each study visit day.

At the completion of 4 weeks of treatment (Day 28), each patient's safety data (e.g., AEs, laboratory values, vital signs, and ECGs) will be reviewed by the Aclaris medical monitor and Aclaris safety physician to ensure that the patient is tolerating the treatment regimen and is deemed suitable to continue treatment for the next 8 weeks.

On Day 84 (Week 12), patients will complete the end of study assessments. A safety follow-up visit will be conducted 30 days (+7) after the last dose of study medication.

The study is randomized and blinded to the investigator, patient, site personnel, and sponsor representatives responsible for clinical monitoring at the investigational to prevent bias in treatment allocation and in the assessment of treatment effect. The Aclaris statistician, medical and safety monitor will be unblinded to each patient's treatment assignment.

Study Duration:

The start of the study will be the date on which the first patient provides informed consent, and the end of the study will be the date of the last patient's last assessment.

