19. Any joint procedure in the past 90 days prior to screening.
20. Known exposure to an individual with a confirmed diagnosis of COVID-19 at any time during the screening period.
21. Vaccination with a live or attenuated vaccine within 6 weeks prior to Baseline (Visit 2) or planned vaccination with these vaccines at any time during treatment or within 6 weeks following discontinuation of study medication.

Test Product:

Name: ATI-450 (50 mg)

Dose: 50 mg BID

Mode of administration: Oral tablets

Concomitant Product

Name: Methotrexate (MTX)

Dose: Patients are to remain on their stable dose of MTX (defined as 7.5 mg to 25 mg per week) throughout the 12-week treatment period

Mode of administration: Oral tablets

Control Product:

Name: Placebo

Dose: 0 mg; administered BID

Mode of administration: Oral tablets

Statistical Methods:

Details of all statistical summaries will be provided in the study-specific statistical analysis plan (SAP).

Analyses will be performed using SAS® (SAS Institute, Cary, NC, US) by the sponsor or its representatives.

The SAP will be approved prior to any lock of the study database and unblinding of the study data. The SAP will provide a detailed description of the statistical methods and expand on the details provided in the protocol.

All data will be presented by treatment group. Descriptive statistics (number of observations, mean, standard deviation, median, minimum, and maximum) will be provided for continuous variables, and counts and percentages will be presented for categorical variables.

Baseline is defined as the last non-missing measurement before or on the date of first administration of study medication.

Determination of Sample Size

The sample size for this study was determined based upon feasibility constraints as opposed to a formal power computation. Approximately 25 patients are planned to be enrolled with the expectation that at least 15 patients will complete the 12-weeks of treatment.

Interim Analyses

This study is being conducted as a sponsor-unblinded study. The safety and efficacy will be assessed on an ongoing basis during the conduct of the trial via multiple unblinded interim analyses. The frequency of the interim analyses will be approximately weekly depending upon the rate of enrollment. Since there is no formal statistical hypothesis, there will be no alpha spending adjustment made for multiple analyses. There is no scenario for which the study would be stopped early for efficacy.

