After 4 weeks of treatment (Day 28), each patient's safety data (e.g., AEs, laboratory values, vital signs, ECGs) will be reviewed by the Aclaris medical monitor and the Aclaris safety physician to ensure that the patient is tolerating the treatment regimen and is deemed suitable to continue treatment for the next 8 weeks. This review is described in more detail in the study-specific safety management plan.

End of study assessments will be conducted on Day 84 (Week 12). A safety follow-up visit will be conducted 30 days (+7 days) after the last dose of study medication.

The study is randomized and blinded to the investigator, patient, site personnel and Aclaris clinical monitors involved in site and patient monitoring with regard to ATI-450 and placebo to prevent bias in treatment allocation and in the assessment of treatment effect. See [Section 6.2](#) for details on access to the treatment codes in the event of emergency unblinding. The Aclaris statistician, medical and safety monitor will be unblinded to each patient's treatment assignment.

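### In a sponsor-unblinded trial with roughly weekly unblinded analyses, does tying SAP approval to 'unblinding' let the analysis rules be settled after the data are seen?

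*Combined protocol and SAP*

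**What the plan says.** The approval milestone appears twice in the same words, in Section 8.1 (General Procedures) and in the synopsis under Statistical Methods. Both state of the SAP that it "will be approved prior to any lock of the study database and unblinding of the study data". Neither place gives a date or refers to the interim analyses.

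The synopsis paragraph on interim analyses opens with the blinding status: "This study is being conducted as a sponsor-unblinded study". Next it describes what the sponsor will look at: "The safety and efficacy will be assessed on an ongoing basis during the conduct of the trial via multiple unblinded interim analyses". On how often, it says: "The frequency of the interim analyses will be approximately weekly depending upon the rate of enrollment". It adds that there is no formal hypothesis and no alpha spending, and it closes with a statement on stopping: "There is no scenario for which the study would be stopped early for efficacy".

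The synopsis, Section 3.1 and Section 6.2 name the unblinded roles: "The Aclaris statistician, medical and safety monitor will be unblinded to each" (that is, to every individual assignment). Investigators, patients, site staff and the sponsor's clinical monitors stay blinded. Section 9.4 says there is no data monitoring committee.

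**The concern.** In a conventionally blinded trial the milestone is clear: the code is broken once, around database lock, and the SAP is signed before that. Here no later code break is described for the sponsor statistician or for the medical and safety monitors. The word unblinding could therefore mean the first unblinded analysis, or a formal release at the end.

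On the second meaning, most of the trial could be seen by arm before the analysis rules were signed off. The conclusion at stake is the one in Section 1.2: a CRP reduction kept up over 12 weeks would distinguish MK2 inhibition from p38 inhibition, for which CRP returned to baseline within 4 to 8 weeks. With no test planned, that conclusion depends on how a sustained effect is read. A reader would want to know that the reading was chosen before the medians by arm were known.

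**Working it through.** The plan gives no alpha, power, effect size or standard deviation, and its sample size is feasibility-based, so there is no plan figure to reproduce. The check compares the two readings, counts the looks, and asks what the SAP still has to settle.

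**1. The two readings.**
- As written: approval comes before any lock and unblinding, hence before whichever is earlier. The synopsis itself calls the interim analyses unblinded, so the first of them is an unblinding of study data. Approval is due before it. If the statistician's access to the codes counts as unblinding, approval is due earlier still.
- Late: approval comes before a final release paired with lock. This requires inserting 'final' before 'unblinding'.

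Only the late reading causes harm.

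**2. Number of looks under the late reading.** Treatment lasts 84 days. Section 3.1 adds the last visit: "A safety follow-up visit will be conducted 30 days (+7 days) after the last dose of study medication".
- Weekly looks up to follow-up if all patients start together: (84 + 30)/7 = 114/7 = 16.3. With the 7-day window: 121/7 = 17.3.
- Looks before Day 84: 84/7 − 1 = 11.
- Staggered entry: the protocol gives no accrual time. Assuming 13, 26 or 52 weeks, looks before the last patient's Day 84 number accrual + 12 − 1 = 24, 37 or 63.

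**3. How much hsCRP information those looks carry.** The Schedule of Assessments draws hsCRP after baseline on Days 7, 14, 28, 42, 56 and 84 and at follow-up: seven draws per patient. If all start together, 16 looks see at most seven new sets of hsCRP data. Sixteen is also not a floor, because the stated frequency is approximate and depends on enrollment, which would already be over in that scenario. Per-Protocol membership requires the Day 84 visit, so the 11 looks before Day 84 could show interim medians but not the determination the plan specifies. With staggered entry, early completers would reach Day 84 sooner and more looks would bring new data.

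**4. What is fixed without the SAP** (synopsis, Efficacy Analyses and Analysis Populations; Section 8.1; Schedule of Assessments).
- Measure: percent change from baseline in hsCRP.
- Summary for the sustained effect: the median over time.
- Population: Per-Protocol, defined by the Day 84 visit and at least 6 of 7 valid hsCRP values. All efficacy summaries are also given for ITT.
- Baseline: the last non-missing value on or before the date of first dose.
- Visits: as scheduled, all tabulated.

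Still open in the readable text are the pattern of medians that counts as sustained and what makes an hsCRP value valid. Section 1.2 narrows the first: a return to baseline by 4 to 8 weeks (Days 28 to 56) is the pattern to be excluded, and the medians at Days 28, 42, 56 and 84 will be on display.

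**5. Group sizes.** At 3:1, 25 patients give 18.75 and 6.25, about 19 and 6. The 15 expected completers give 11.25 and 3.75, about 11 and 4. These numbers suit description only, which is what the plan proposes.

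**The case for a change.** The strongest argument for a change is that a descriptive trial depends more on prespecification, not less. No test disciplines the conclusion, no independent committee exists, and the sponsor or its representatives run the analyses. The date on which the rules were fixed is then the main safeguard, and stating it takes two sentences.

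A simulation can put a size on the freedom involved. Suppose CRP falls early and is fully back at baseline by Day 28, 42 or 56, with 11 active completers. Assume a standard deviation of log(hsCRP/baseline) of 0.6 to 0.9, within-patient correlation of 0.3 to 0.7, and a true early fall of 40 to 60%; none of these comes from the documents. Take three readings of sustained: all six post-baseline medians below zero; a Day 84 median of −20% or lower; a Day 84 fall at least half the best earlier fall. If any of the three may be chosen afterwards, the effect is wrongly called sustained in 22 to 37% of trials. That is 3 to 11 percentage points above the most lenient single reading in the same setting. With 19 active patients the gain is 1 to 12 points.

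Part of this stands. The milestone is loosely worded for this design, and the readable text does not define sustained. But the simulation contains no interim looks, so it measures the undefined term and not the timing of approval: a single look at the end gives the same figures. Nor would moving the date close that gap, since a SAP signed on day one could leave all three readings open. The cost also exceeds two sentences, because Section 12 makes any permanent protocol change an amendment that must await IRB/IEC approval.

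**Conclusion.** No change follows. The sentence, taken at its word, already requires approval before the first unblinded analysis. A sponsor who follows it obtains a sound descriptive result, and a rewrite would only spell out that reading. The main choices for hsCRP are in the protocol, and both ITT and Per-Protocol results will be shown over time. hsCRP is a secondary endpoint measured centrally, and patients and investigators remain blinded. With no hypothesis test and no efficacy stopping, no type I error rate is affected.

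The weight is minor. The count of about 16 looks applies only under the late reading, a strict weekly cadence and simultaneous entry, and even then it corresponds to seven post-baseline hsCRP draws per patient. The 3 to 11 point figure belongs to a different question, the meaning of sustained.

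This conclusion assumes that the sponsor applies the sentence literally. The file cannot confirm that: Sections 8.2 to 8.4.1 are not readable, no separate SAP is included, and neither the SAP's approval date nor the date of the first look is given. Silence in the readable text is therefore weak evidence of a gap.
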